5.2. General Methods

As described in Section 3.4, in this study ‘**treatment group**’ refers to:

- Phase 1b Sub-Study A Dose Level 0: sasanlimab 300mg + encorafenib 300mg + binimetinib 45mg

- Phase 1b Sub-Study A Dose Level 1: sasanlimab 300mg + encorafenib 450mg + binimetinib 45mg
- Phase 1b Sub-Study A Dose Level -1: sasanlimab 300mg + encorafenib 300mg + binimetinib 30mg
- Phase 2 Sub-Study A: To be determined from Phase 1b
- Phase 1b Sub-Study B: sasanlimab CCI + axitinib 5 mg BID
- Phase 1b Sub-Study B: sasanlimab CCI + axitinib 3 mg BID
- Phase 1b Sub-Study B: sasanlimab CCI + axitinib 5 mg BID + SEA- TGT DL0
- Phase 1b Sub-Study B: sasanlimab CCI + axitinib 5 mg BID + SEA- TGT DL1
- Phase 1b Sub-Study B: sasanlimab CCI + axitinib 5 mg BID + SEA- TGT DL-1
- Phase 1b Sub-Study B: sasanlimab CCI + axitinib 3 mg BID + SEA- TGT DL0
- Phase 1b Sub-Study B: sasanlimab CCI + axitinib 3 mg BID + SEA- TGT DL1
- Phase 1b Sub-Study B: sasanlimab CCI + axitinib 3 mg BID + SEA- TGT DL-1
- Phase 2 Sub-Study B: To be determined from Phase 1b

The following will be provided by sub-study and corresponding treatment groups.

Baseline characteristics, disposition, and efficacy data will be summarized based on the FAS by sub-study and treatment group.

DLTs will be summarized based on the DLT-evaluable set by sub-study and treatment group including data from Phase 1b only.

Other safety data, exposure data, concomitant medications and non-drug treatments will be summarized based on the safety analysis set by sub-study and treatment group.

PK data will be summarized based on the PK analysis set by sub-study and treatment group.

Biomarker data will be summarized based on the biomarker analysis set by sub-study and treatment group.

Immunogenicity data will be summarized based on the immunogenicity analysis set by sub-study and by treatment group, if data permit.

5.2.1. Data handling after the cut-off date

Data after the cut-off date may not undergo the cleaning process and will not be displayed in any listings or used for summary statistics, statistical analyses or imputations.

5.2.2. Pooling of centers

In order to provide overall estimates of treatment effects, data will be pooled across centers. The 'center' factor will not be considered in statistical models or for subgroup analyses due to the high number of participating centers in contrast to the anticipated small number of participants treated at each center.

5.2.3. Presentation of continuous and qualitative variables

Continuous variables will be summarized using descriptive statistics i.e., number of non-missing values and number of missing values [i.e., n (missing)], mean, median, standard deviation (SD), minimum, maximum and first and third quartile (Q1 and Q3).

Qualitative variables will be summarized by frequency counts and percentages. Unless otherwise specified, the calculation of proportions will include the missing category. Therefore, counts of missing observations will be included in the denominator and presented as a separate category.

In case the analysis refers only to certain visits, percentages will be based on the number of participants still present in the study at that visit, unless otherwise specified.

5.2.4. Definition of study day

Start day of study treatment is the day of the first dose of study treatment.

The study day for assessments occurring on or after the start of study treatment (e.g., adverse event onset, tumor measurement) will be calculated as:

$$\text{Study day} = \text{Date of the assessment/event} - \text{start of study treatment} + 1.$$

The study day for assessments occurring prior to the first dose of study treatment (e.g., baseline characteristics, medical history) will be negative and calculated as:

$$\text{Study day} = \text{Date of the assessment/event} - \text{start of study treatment}.$$

The study day will be displayed in all relevant data listings.

5.2.5. Definition of start of new anti-cancer drug therapy

Start date of new anti-cancer drug therapy is used to determine the end of the on-treatment period (see Section 5.2.7).

The start date of new anti-cancer drug therapy is the earliest start date of anti-cancer drug therapy recorded in the 'Follow-up Cancer Therapy' or 'Concomitant Medication' eCRF pages that is after the first dose of study treatment. When start date of anti-cancer drug therapy is missing or partially missing, the imputation rules described in Section 5.3.3.4 should be applied using only data from the 'Follow-up Cancer Therapy' eCRF pages.

5.2.6. Definition of start of new anti-cancer therapy

Start date of new anti-cancer therapy (drug, radiation, surgery) is used for censoring in efficacy analyses (see Section 6.1.2 and Section 6.2.2).

The start date of new anti-cancer therapy is the earliest date after the first dose of study treatment amongst the following:

- Start date of anti-cancer drug therapy recorded in the 'Follow-up Cancer Therapy' eCRF pages

- Start date of radiation therapy recorded in ‘Radiation Therapy’ eCRF pages with ‘Treatment Intent’ = ‘Curative in intent’
- Surgery date recorded in ‘On Study Follow up Cancer Surgery’ eCRF pages when ‘Surgery Outcome’ = ‘Resected’ or ‘Partially Resected’.

When start date of anti-cancer therapy is missing or partially missing, the imputation rules described in Section 5.3.3.4 should be applied using ‘Follow-up Cancer Therapy’, ‘Radiation Therapy’, ‘On Study Follow up Cancer Surgery’ eCRF pages.

5.2.7. Definition of on-treatment period

Safety endpoints will be summarized based on the on-treatment period unless otherwise specified.

On-treatment period is defined as the time from the first dose of study treatment through minimum (30 days + last dose of study treatment, start day of new anti-cancer drug therapy – 1 day).

Safety data collected outside the on-treatment period as described above will be listed and flagged in listings but not summarized.

5.2.8. Standard derivations and reporting conventions

The following conversion factors will be used to convert days into weeks, months or years: 1 week = 7 days, 1 month = 30.4375 days, 1 year = 365.25 days.

Demographics and physical measurements:

Age [years]: (year of given informed consent - year of birth)

The integer part of the calculated age will be used for reporting purposes.

For reporting conventions, mean and median should generally be displayed one more decimal place than the raw data and standard deviation should be displayed to two more decimal places than the raw data. Percentages will be reported to one decimal place. The rounding will be performed to closest integer / first decimal using the common mid-point between the two consecutive values. E.g., 5.1 to 5.4 will be rounded to an integer of 5, and 5.5 to 5.9 will be rounded to an integer of 6.

5.2.9. Unscheduled visits

Generally, data collected at unscheduled visits will be included and analyzed for both safety and efficacy analyses in the same fashion as the data collected at scheduled visits except where otherwise noted in the sections that follow. Descriptive statistics (mean, SD, median, minimum, maximum, quartiles) by nominal visit or time point for safety endpoints such as laboratory measurements, ECGs and vital signs will include only data from scheduled visits (if such analyses are performed).

5.2.10. Adequate baseline tumor assessment

Adequate baseline is defined using the following criteria:

- All baseline assessments must be within 28 days prior to and including the date of first dose of study treatment.
- All documented lesions must have non-missing assessments (i.e., non-missing measurements for target lesions and non-missing lesions assessment status at baseline for non-target lesions).

5.2.11. Adequate post-baseline tumor assessment

An adequate post-baseline assessment is defined as an assessment where a response of CR, PR, SD, non-CR/non-PD, or PD can be determined (see Section 6.2.2.1). Time points where the response is not evaluable (NE) or no assessment was performed will not be used for determining the censoring date.

5.3. Methods to Manage Missing Data

5.3.1. Missing data

Unless otherwise specified, all data will be evaluated as observed, and no imputation method for missing values will be used.

In all participant data listings imputed values will be presented. In all listings imputed information will be flagged.

Missing statistics, eg when they cannot be calculated, should be presented as 'ND' or 'NA'. For example, if N=1, the measure of variability (SD) cannot be computed and should be presented as 'ND' or 'NA'.

5.3.1.1. Pharmacokinetic concentrations

Concentrations Below the Limit of Quantification

In all data presentations (except listings), concentrations below the limit of quantification (BLQ) will be set to zero. In listings, BLQ values will be reported as "<LLQ", where LLQ will be replaced with the value for the lower limit of quantification.

Deviations, Missing Concentrations and Anomalous Values

In summary tables and plots of median profiles, concentrations will be set to missing if one of the following cases is true:

1. A concentration has been reported as ND (i.e., not done) or NS (i.e., no sample);
2. A deviation in sampling time is of sufficient concern or a concentration has been flagged as anomalous by the clinical pharmacologist.

Summary statistics will not be presented at a particular time point if more than 50% of the data are missing.

5.3.1.2. Pharmacokinetic parameters

Whether actual or nominal PK sampling time will be used for the derivation of PK parameters will be determined by the results of interim PK analyses. If a PK parameter cannot be derived from a participant's concentration data, the parameter will be coded as NC (i.e., not calculated). NC values will not be generated beyond the day that a participant discontinues.

In summary tables, statistics will be calculated by setting NC values to missing. Statistics will not be presented for a particular treatment if more than 50% of the data are NC. For statistical analyses (i.e., analysis of variance), PK parameters coded as NC will also be set to missing.

If an individual participant has a known biased estimate of a PK parameter (due for example to a deviation from the assigned dose level), this will be footnoted in summary tables and will not be included in the calculation of summary statistics or statistical analyses.

5.3.2. Handling of incomplete dates

5.3.2.1. Disease history

Incomplete dates for disease history (e.g., initial diagnosis date, date of documented, locally advanced, inoperable or metastatic disease diagnosis, date of response or progression in prior treatment) will be imputed as follows:

- If the day is missing, it will be imputed to the 15th day of the month.
- If both day and month are missing and the year is prior to the year of the first study treatment, the month and day will be imputed as July 1st.
- If both day and month are missing and the year is same as the year of the first study treatment, the month and day will be imputed as January 1st.
- If the date is completely missing, no imputation will be performed.

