6.5.1.3. Disease characteristics

Information on disease characteristics collected on ‘Primary Diagnosis’, ‘Substance Use’ and RECIST eCRF pages will be summarized overall and by treatment group. Summary statistics will be presented for the following.

From the ‘Primary Diagnosis’ eCRF page:

- Site of primary tumor
- Primary diagnosis (summarize all categories collected in the ‘Primary Diagnosis’ eCRF page)
- Time since initial diagnosis to date of first dose of study treatment (months), defined as (date of first dose of study treatment – date of initial diagnosis)/30.4375

From the RECIST eCRF page:

- Measurable disease (lesions) at baseline (Yes, No)
- Involved tumor sites at baseline

From the ‘Substance Use’ eCRF page:

- Smoking history (never smoker vs current vs former smoker)

Listing of disease history will be provided with all relevant data (as collected on the ‘Primary Diagnosis’ eCRF page) and derived variables as above. Brain metastasis at baseline will be reported as yes/no.

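### A disease-history date with a missing day is set to the 15th with no check against first dose, so time since initial diagnosis can come out negative

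*SAP*

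**What the plan says.** SAP Section 5.3.2.1 covers incomplete dates of initial diagnosis, of advanced or metastatic diagnosis, and of response or progression on prior treatment. Three of its rules matter here:

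- Month and year known: "If the day is missing, it will be imputed to the 15th day of the month".
- Only the year known, earlier than the treatment year: "the year is prior to the year of the first study treatment, the month and day will be imputed as July 1st".
- Only the year known, equal to the treatment year: "the year is same as the year of the first study treatment, the month and day will be imputed as January 1st".

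The two year-only rules look at the year of first dose. The missing-day rule looks at nothing outside the partial date.

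Section 6.5.1.3 lists time since initial diagnosis among the disease characteristics to be summarised overall and by treatment group, "defined as (date of first dose of study treatment – date of initial diagnosis)/30.4375". It sets no lower limit. Section 5.2.3 includes the minimum and the mean in the standard summary of a continuous variable. Section 5.3.1 has imputed values shown and flagged in participant listings.

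**The concern.** A diagnosis that qualifies a participant for the trial cannot come after the first dose. A fixed mid-month date can break that order whenever the partial date falls in the month of first dose. The derived interval is then an impossible value. A single case would appear as the minimum in the baseline table, and the listing would show a diagnosis dated after treatment start.

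The year-only rules avoid this outcome, since neither 1 July of an earlier year nor 1 January of the treatment year can fall after first dose. The missing-day rule has no such protection, and nothing elsewhere in the SAP supplies it.

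What is at stake is the tidiness and credibility of one descriptive variable. It is better to settle this in the rule than to correct it case by case once data are seen.

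**Working it through.** The SAP gives no figure on this point, so there is nothing to reproduce. The check applies the stated rules to the stated formula.

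**Inputs**
- Imputed day when the day is missing: 15 (Section 5.3.2.1).
- Interval in months: first dose minus diagnosis, in days, divided by 30.4375 (Section 6.5.1.3). Section 5.2.8 gives the same conversion, "1 month = 30.4375 days".

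**Missing day, same month and year as first dose**

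Let f be the day of the month of first dose. The interval is (f - 15)/30.4375 months.

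| First dose on day | Days | Months |
|---|---|---|
| 1 | -14 | -0.46 |
| 5 | -10 | -0.33 |
| 10 | -5 | -0.16 |
| 14 | -1 | -0.03 |
| 15 | 0 | 0.00 |
| 28 | +13 | +0.43 |

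The result is negative for every f from 1 to 14. That is 12 × 14 = 168 of the 365 possible first-dose days in a year (46%). This is a share of calendar days given a same-month partial date, not a share of participants.

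If the recorded month is before the month of first dose, the 15th always precedes first dose and no negative value can arise.

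**Effect on a group mean**

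If the true diagnosis was on the 1st, one such case understates the interval by 14 days, the largest possible error when f is 14 or less. In a group of 20 this moves the mean by 14/20 = 0.7 days (0.02 months). In a cohort of 3 it moves it by 14/3 = 4.7 days (0.15 months).

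**With the date capped at first dose**

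For f from 1 to 14 the interval becomes 0, so the minimum moves from -14 days to 0. The true value then lies between 0 and f - 1 days, so the remaining error is at most 13 days (0.43 months) and the value is no longer impossible.

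**Year-only date in the treatment year (the optional point)**

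The imputed interval is (first dose - 1 January)/30.4375. The largest possible overstatement equals the whole interval, when diagnosis was on the day of first dose.

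| First dose | Imputed interval = largest overstatement (months) | Midpoint rule (months) |
|---|---|---|
| 31 January | 30/30.4375 = 0.99 | 0.49 |
| 30 June | 180/30.4375 = 5.91 | 2.96 |
| 31 December | 364/30.4375 = 11.96 | 5.98 |

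The interval is never understated and never negative.

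**The case against.** The strongest reply is that this hardly matters. A negative value needs three things together: a missing day, a date in the calendar month of first dose, and dosing on days 1 to 14. Even then it is at most 14 days below zero. Section 3.4.2 does not plan baseline characteristics as covariates or stratification variables, time since diagnosis is not a subset in Section 6.4, and imputed values are flagged in listings. All of this stands and sets the size of the point. It does not remove the point, because the rule as written still yields an impossible value and no other section corrects it.

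Several stronger readings are tempting, and the SAP does not support them:

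- **Comparability of Arms B1, B2 and B3.** A reader might infer that the error distorts a comparison between small arms. The SAP plans no such comparison. The arms are non-randomised, and Section 5.1.1.2 sizes each to estimate its own response rate. Nor does having had no prior therapy for advanced disease mean that the initial diagnosis was recent.
- **The 1 January rule as a second error.** It is one-sided, but it is coherent: it is a fixed date that cannot fall after first dose. Preferring a midpoint is a choice. An average overstatement of about 3.0 months can be calculated, but only if true dates are uniform between 1 January and first dose and first doses are also spread evenly over the year.
- **Metastatic and prior-progression dates.** An imputed date could fall out of order with a recorded one, but Section 6.5.1.3 derives no interval from these dates, so the effect stops at a listing.
- **The adverse event and medication rules as a model.** Sections 5.3.2.2 and 5.3.2.3 do tie same-month dates to treatment start, but those dates bear on treatment-emergent or concomitant status. They show that the SAP uses such a check, not that the purpose is the same.

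**Conclusion.** The missing-day rule in Section 5.3.2.1 lacks a limit at first dose. For a partial date in the month of first dose, with dosing on days 1 to 14, time since initial diagnosis can be -1 to -14 days (-0.03 to -0.46 months). This follows from the SAP's own rule and formula and needs no assumption beyond such a partial date occurring.

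How often that happens is unknown, since the SAP does not give the number of partial dates; it is probably uncommon. The consequence is limited to a descriptive summary and the listed dates. No endpoint, hypothesis test or censoring rule depends on it. This is a minor correction worth making because it is so cheap.

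The 1 January convention for year-only dates is a matter of preference. It can overstate the interval by up to 11.96 months for an individual, in the extreme case of diagnosis and first dose both on 31 December.

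**What to change.** In Section 5.3.2.1, amend the first rule so that a date with only the day missing is imputed to the earlier of the 15th of the recorded month and the date of first dose. The cap should be first dose itself and not the day before: with first dose on the 1st, the day before would move the date out of the recorded month. A recorded month later than that of first dose is a data error and should go to query, so that the cap does not hide it.

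Optional: for year-only dates in the treatment year, replace 1 January with the midpoint between 1 January and first dose. If true dates are uniform over that interval, the mean error is then about zero.

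The cost is one clause of SAP wording and a line or two of derivation code for each change. No sample size, endpoint or data collection is affected.

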5.3.2.2. Adverse events

Incomplete AE-related dates will be imputed as follows:

- If the AE onset date is missing completely, then the onset date will be replaced by the start of study treatment.
- If only the day part of the AE onset date is missing, but the month and year are equal to the start of study treatment, then the AE onset date will be replaced by the start of study treatment. For example, if the AE onset date is --/JAN/2015, and study treatment start date is 15/JAN/2015, then the imputed AE onset date will be 15/JAN/2015.
- If both the day and month of the AE onset date are missing but the onset year is equal to the start of study treatment, then the onset date will be replaced by the start of study treatment. For example, if AE onset date is --/--/2014, and study treatment start date is 19/NOV/2014, then the imputed AE onset date will be 19/NOV/2014.
- In all other cases the missing onset day or missing onset month will be replaced by 1.

- Incomplete stop date will be replaced by the last day of the month (if day is missing only), if not resulting in a date later than the date of participant 's death. In the latter case the date of death will be used to impute the incomplete stop date.
- In all other cases the incomplete stop date will not be imputed. If stop date of AE is after the date of cut-off outcome of AE is ongoing at cut-off.

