3.5. Safety Endpoints

3.5.1. Adverse events

Treatment-Emergent Adverse Events

Treatment-emergent adverse events (TEAEs) are those events with onset dates occurring during the on-treatment period.

On-treatment period is defined as the time from the first dose of study treatment through minimum (30 days + last dose of study treatment, start day of new anti-cancer drug therapy – 1 day). The start day of new anti-cancer drug therapy after the first dose of study treatment is derived as outlined in Section 5.2.5.

Adverse Events of Special Interest (AESIs)

AESIs are immune-related adverse events (irAE). The criteria for classification of an AE as an irAE are described in Appendix 1.

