5.3.2.3. Prior and concomitant medications

Incomplete prior/concomitant medication dates will be imputed as follows:

- If the medication date is missing completely, then the medication date will be replaced by the start of study treatment.
- If the day of medication date is missing, but the month and year are equal to the start of study treatment, then the medication date will be replaced by the start of study treatment. For example, if the medication start date is --/JAN/2015, and study treatment start date is 15/JAN/2015, then the imputed medication start date will be 15/JAN/2015.
- If both the day and month of medication start date are missing but the start year is equal to the start of study treatment, then the medication date will be replaced by the start of study treatment. For example, if the medication start date is --/---/2014, and study treatment start date is 19/NOV/2014, then the imputed medication start date will be 19/NOV/2014.
- In all other cases the missing medication day or missing medication month will be replaced by 1.
- Incomplete stop date will be replaced by the last day of the month (if day is missing only), if not resulting in a date later than the date of participant 's death. In the latter case the date of death will be used to impute the incomplete stop date.
- In all other cases the incomplete medication stop date will not be imputed.

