6.5.4. Concomitant medications and non-drug treatments

The following analyses will be based on the safety analysis set by treatment group.

Concomitant medications are medications, other than study drugs, which started prior to first dose date of study treatment and continued during the on-treatment period as well as those started during the on-treatment period. **Prior medications** are medications, other than study drugs and pre-medications for study drug, which are started before the first dose of study treatment.

Concomitant medications will be summarized from the ‘Concomitant Medications’ eCRF page.

Summary of concomitant medications will include the number and percentage of participants by Anatomical Therapeutic Chemical (ATC) Classification level 2 and preferred term. A participant will be counted only once within a given drug class and within a given drug name, even if he/she received the same medication at different times. If any concomitant medication is classified into multiple ATC classes, the medication will be summarized separately under each of these ATC classes. The summary tables will be sorted on decreasing frequency of drug class and decreasing frequency of drug name in a given drug class. In case of equal frequency regarding drug class (respectively drug name), alphabetical order will be used. In case any specific medication does not have ATC classification level 2 coded term, it will be summarized under ‘Unavailable ATC classification’ category.

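### Three imputation rules move missing AE onset and medication start dates to first dose even when a recorded stop date shows the record ended before treatment

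*SAP*

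**What the plan says.** Section 5.3.2.2 of the SAP has four rules for an incomplete AE onset date. Three of them return the first-dose date:

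- Completely missing onset: "If the AE onset date is missing completely, then the onset date will be replaced by the start of study treatment".
- Day missing, month and year matching: "If only the day part of the AE onset date is missing, but the month and year are equal to the start of study treatment".
- Day and month missing, year matching: "If both the day and month of the AE onset date are missing but the onset year is equal to" that of first dose.

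The fourth covers everything else: "In all other cases the missing onset day or missing onset month will be replaced by 1".

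Stop dates have their own rule. One lacking only the day goes to the end of its month, limited by the date of death. A stop date lacking more than the day is left unimputed. The stop date is never compared with the imputed onset.

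Section 5.3.2.3 gives the same set of rules for medications, beginning with "If the medication date is missing completely, then the medication date will be replaced by the start of study treatment".

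The classifications that use these dates are:

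- **TEAEs (3.5.1):** "Treatment-emergent adverse events (TEAEs) are those events with onset dates occurring during the on-treatment period". Sections 3.5.1 and 5.2.7 both open that period at first dose.
- **Concomitant medications (6.5.4):** drugs begun earlier and continued into the on-treatment period, "as well as those started during the on-treatment period". Prior medications must have started before first dose.
- **irAEs (Appendix 1, Table 15, step 2):** onset must be on or after first dose and no later than 90 days after the last dose.

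**The concern.** Putting an unknown onset at first dose is sensible when the timing really is unknown. It is not sensible when the stop date is recorded and precedes first dose. The timing relative to treatment is then known, and the rule overrides it, leaving a record that starts after it stopped.

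A resolved pre-treatment event would be counted in the TEAE tables. It would also enter the related-TEAE tables if marked related or if the relationship was left blank, because 6.6.1 counts a blank as related. It would meet the onset condition of the irAE definition. A drug already stopped would be tabulated as concomitant. Only descriptive safety and medication summaries are at stake. No primary endpoint, hypothesis test or decision rule uses TEAE or concomitant status.

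**Working it through.** The SAP states no figure here to reproduce. The check applies its rules literally to test records.

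**Inputs.** The onset patterns and first-dose dates in records (a) to (c) follow 5.3.2.2, whose own examples use first doses of 15/JAN/2015 and 19/NOV/2014. The stop dates are assumed for illustration.

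**Rule as written.** Imputed onset = first dose for the three patterns; otherwise the missing part is set to 1. TEAE if imputed onset ≥ first dose (all test dates lie before the end of the on-treatment period).

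| Record | Onset | First dose | Stop (assumed) | Imputed onset | TEAE? |
|---|---|---|---|---|---|
| a | all missing | 15JAN2015 | 10JAN2015 | 15JAN2015 | yes |
| b | --/JAN/2015 | 15JAN2015 | 10JAN2015 | 15JAN2015 | yes |
| c | --/--/2014 | 19NOV2014 | 30JUN2014 | 19NOV2014 | yes |
| d | --/DEC/2014 | 15JAN2015 | 10JAN2015 | 01DEC2014 | no |
| e | --/--/2013 | 19NOV2014 | 30JUN2014 | 01JAN2013 | no |
| f | all missing | 15JAN2015 | 20JAN2015 | 15JAN2015 | yes |

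In (a) and (b) the imputed onset falls 15 − 10 = 5 days after the event ended. In (c) it falls 142 days after (30 June to 19 November). All three are misclassified. Records (d) and (e) show that the fourth rule keeps earlier-month and earlier-year dates before treatment. Record (f) is classified as the convention intends.

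The same dates entered as medications behave the same way: (a) to (c) count as started in the on-treatment period, so they are concomitant and no longer prior.

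**With a cap.** Imputed onset = min(rule's date, stop date):

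- (a) and (b): min(15JAN2015, 10JAN2015) = 10JAN2015, not a TEAE.
- (c): min(19NOV2014, 30JUN2014) = 30JUN2014, not a TEAE.
- (f): min(15JAN2015, 20JAN2015) = 15JAN2015, still a TEAE.

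The cap therefore changes only the records whose stop date contradicts the imputation.

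**Size per participant.** In a group of 62 (planned Phase 2, Sub-Study A), one participant is 1/62 = 1.6%. Section 6.6.1 counts each participant once per SOC or PT, so this is the most one participant can add to a row, and only if that participant has no other qualifying event there.

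**The case against.** The strongest reply is that imputing to first dose is a common convention that deliberately errs towards over-counting TEAEs, the cautious direction for safety. That stands where the stop date is missing or falls on or after first dose. It does not stand where the stop date already settles the question.

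The misclassification is also narrow. It needs one of three missing-date patterns together with a known stop date before first dose. For AEs, the event must also have been collected before first dose, and the start of AE collection is a matter for the protocol. All of that stands and keeps the point small. The medication side is somewhat firmer, because 6.5.4 expects drugs that were started before first dose.

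There are partial safeguards. Section 5.3.1 flags imputed values in listings, and Appendix 1 lets medical review refine the irAE set. Neither corrects the TEAE or concomitant-medication tables.

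Three stronger readings are tempting, and the document does not support them:

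- A reader might infer that negative durations will reach the results. The SAP plans no AE-duration or medication-duration output, so a stop before its start is a data inconsistency and not a wrong table.
- A reader might infer that every missing or partial date goes to first dose. The fourth rule in both sections prevents that.
- A reader might see a contradiction with 5.3.3.4, which caps the imputed start of new anti-cancer therapy at its end date. That rule serves efficacy censoring and the end of the on-treatment period. It shows that the device is available in this SAP, not that the SAP conflicts with itself.

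**Conclusion.** The point holds in limited form. For three patterns of missing date, sections 5.3.2.2 and 5.3.2.3 give a wrong classification whenever the recorded stop date is before first dose, and nothing elsewhere in the SAP corrects it. Affected records become TEAEs, and can pass step 2 of the irAE definition, or become concomitant medications.

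The total effect cannot be estimated, because the SAP gives no count of such records; it is probably small. The ceiling of 1.6 points per misclassified participant assumes a group of 62 and no other event for that participant in the row. In the overall TEAE row, one extra record will often change nothing. This is a minor drafting correction to descriptive summaries.

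**What to change.** Add one clause to each of 5.3.2.2 and 5.3.2.3:

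- Apply the impute-to-first-dose rules only if the stop date is missing or could fall on or after first dose.
- If the stop date is before first dose, set the imputed onset or start to the earlier of the rule's date and the stop date, so that the record stays pre-treatment.
- For a partial stop date, use its last possible day in both steps: the last day of the month if only the day is missing, or 31 December if only the year is known. The year-only case has to be spelled out, because the present rules leave such stop dates unimputed.

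The cost is two sentences and a small programming change. It needs no new data and leaves the cautious convention in place for every record whose stop date does not rule it out.
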